5.4.1 Long term follow-up assessments

This is a feasibility study and long-term follow-up beyond the 8-week intervention period includes the 3-month, 6-month and 12-month questionnaires to investigate the longer-term impact of the course.

Frequency and duration of follow-up

Participants will be sent questionnaires approximately 2 weeks after completion of the 8-week OurPERSPECTIVE course (3 month); and will be invited to participate in focus group or interviews to approximately 4 weeks after completing of intervention completion. Further long-term follow up will be completed at 6-month and 12-month of intervention completion with the included questionnaires to compare to baseline symptom burden.

Assessments

Post-intervention assessments will include the same questionnaires completed at baseline (SF-36, HADS, EQ-5D-5L, acceptability/usability questions) and an optional focus group.

SPONSOR REFERENCE: 1097

OurPERSPECTIVE endometrial cancer survivorship Study

Protocol Version v1.0 14/10/2025

IRAS: 363748

These measures will capture short-term changes in wellbeing and evaluate the acceptability of the intervention.

Differences from standard care

The course and the assessments are additional to standard NHS follow-up, which typically focuses on clinical surveillance for recurrence and does not include a structured survivorship course, questionnaires or peer-support evaluation.

Retention strategies

Retention will be supported through flexible scheduling of questionnaires (online or postal completion), reminder emails/telephone calls, and provision of modest shopping vouchers as a token of thanks. The focus on short-term follow-up reduces risk of attrition.

Identification of lost to follow-up

Participants will be considered lost to follow-up if they do not return post-intervention questionnaires and cannot be contacted after three attempts (e.g. email, phone, postal reminder).

Handling missed data

If questionnaire time-points are missed, participants will still be invited to complete subsequent assessments where possible. Early-exit data will be recorded if participants withdraw before completing the study.

Data from non-adherers

For participants who discontinue the intervention but do not withdraw consent, available outcome data (e.g. questionnaires completed up to that point) will still be retained and included in feasibility analysis.

5.5 Study intervention(s) and comparator(s)

5.5.1 Description of study intervention

The study intervention is OurPERSPECTIVE, a virtual, group-based survivorship course co-designed with women who have experienced endometrial cancer.

SPONSOR REFERENCE: 1097

OurPERSPECTIVE endometrial cancer survivorship Study

Protocol Version v1.0 14/10/2025

IRAS: 363748

The course will be facilitated by a gynaecology clinical nurse specialist who is part of the UHL direct clinical care team and will be known to the participants. The course will be delivered online via a secure videoconferencing platform (Microsoft Teams). The course will run for 6-8 consecutive weeks, with one session each week lasting approximately 60 minutes. There are 6 core modules for all participants and 2 additional modules (menopause and sexual function) that participants can chose to attend if they wish. Each session combines education, discussion, workbook activities and peer support, and covers the following modules: physical activity, sleep disturbance, body changes, tiredness, fear of recurrence, tiredness, menopause, and sexual disturbance.

At the start of the course, group rules will be established to create a safe and respectful environment. Each session will conclude with a short debrief to check wellbeing and provide closure. The specialist nurse who will be facilitating the course will be able to provide additional support to participants who become distressed or indicate that they need additional support during a session.

Attendance at each session will be recorded in the attendance log. The courses will aim to have 10 women per cohort, with 3 cohorts planned for the feasibility study.

5.5.2 Description of comparator

Not Applicable.

5.6 Expenses and benefits

Participants will not be asked to attend any face-to-face visits outside of routine NHS care. All questionnaires, intervention sessions, and focus groups will be delivered remotely.

To recognise the time and effort required to take part, participants will be offered a shopping voucher (£20 in value) after completion of the study assessments. The voucher may be for a supermarket, high-street store, or coffee shop, according to participant preference, and will be issued once all post-intervention activities are completed.

This is not intended as payment but as a token of appreciation. No reimbursement of travel expenses is required as all activities are virtual.

5.7 Early discontinuation/withdrawal of participants

Participants may withdraw from the study at any point, without giving a reason and without any prejudice to their current or future NHS care.

Withdrawal can take different forms:

SPONSOR REFERENCE: 1097

OurPERSPECTIVE endometrial cancer survivorship Study

Protocol Version v1.0 14/10/2025

IRAS: 363748

- A participant may choose to stop attending the OurPERSPECTIVE course but remain in the study to complete questionnaires and/or the focus group.
- A participant may withdraw fully from all aspects of the study.
- The Principal Investigator may withdraw a participant if it is judged that continued participation would not be in their best interests or exclusionary criteria is later met (e.g. recurrence of cancer, significant health deterioration, or safeguarding concerns).

If a participant withdraws or loses capacity to consent for themselves, data collected up to the point of withdrawal will be retained and included in the study analysis.

No specific safety follow-up procedures are required for participants who withdraw, as this is a low-risk, non-CTIMP feasibility study. However, participants will be asked (where possible) whether they are willing to complete an early-exit questionnaire to capture partial outcome data. The specialist nurses will be aware of the participant's withdrawal and can follow-up if clinical concerns.

The type of withdrawal and reason for withdrawal will be recorded in the CRF and on the subject enrolment log.

5.8 Definition of end of study

For the purposes of this protocol, the end of the study will be taken as the point at which the final participant has completed all study-related activities. In practical terms, this will be the return of the post-intervention questionnaires at the 12-month mark and completion of sample analysis. The study will formally close once the last element of data collection has been completed for the last participant.

6 Sample Handling

Not Applicable.

6.1 Arrangements for sample storage

Not Applicable.

6.2 Arrangements for sample destruction

Not Applicable.

7 Safety Reporting

7.1 Definitions

SPONSOR REFERENCE: 1097

OurPERSPECTIVE endometrial cancer survivorship Study

Protocol Version v1.0 14/10/2025

IRAS: 363748

Term	Definition
Adverse Event (AE)	Any untoward and unintended medical occurrence (including an abnormal laboratory finding), symptom or disease in a participant, whether or not it is considered related to the study.
Adverse Reaction (AR)	
Any untoward and unintended medical occurrence (including an abnormal laboratory finding), symptom or disease in a participant which is considered related to the study.
 
The assessment of expectedness must be undertaken by a delegated medically qualified professional.
 
Where an event could be considered possibly, probably or unlikely related to the study, for the avoidance of doubt, this should be considered related.

Serious Adverse Event (SAE)	
Any untoward and unintended medical occurrence that meets the following serious criteria, whether or not it is considered related to the study:
 
 • results in death • is life-threatening[^] • requires inpatient* hospitalisation or prolongation of existing hospitalisation • results in persistent or significant disability/incapacity, or • is a congenital anomaly/birth defect • Other 'important medical events' may also be considered serious if they jeopardise the participant or require an intervention to prevent one of the above consequences. 
NOTE:
 
[^]The term "life-threatening" in the definition of "serious" refers to an event in which the participant was at risk of death at the time of the event; it does not refer to an event which hypothetically might have caused death if it were more severe.

Serious Adverse Reaction (SAR)	Any untoward and unintended medical occurrence that meets the above referenced serious criteria and, in the opinion of the delegated medically qualified professional, is believed to be related (possibly, probably, unlikely) to the study intervention.
Suspected Unexpected Serious Adverse Reaction (SUSAR)	
Any untoward and unintended medical occurrence that meets the above referenced serious criteria and, in the opinion of the delegated medically qualified professional, is believed to be related to the study intervention but is not listed within the anticipated events section below.
 
Any untoward and unintended medical occurrence that meets the above referenced serious criteria and, in the opinion of the delegated medically qualified professional, is believed to be related to the study intervention. There are no anticipated

SPONSOR REFERENCE: 1097

OurPERSPECTIVE endometrial cancer survivorship Study

Protocol Version v1.0 14/10/2025

IRAS: 363748

	events for this study therefore, any events which are considered related will be considered unexpected.
--	--

NB: to avoid confusion or misunderstanding of the difference between the terms “serious” and “severe”, the following note of clarification is provided: “Severe” is often used to describe intensity of a specific event, which may be of relatively minor medical significance. “Seriousness” is the regulatory definition supplied above.

7.2 Expected Adverse Events/Reactions and Serious Adverse Events/Reactions

Expected events are medical occurrences which are known to occur based on the population/disease being studied. **Expected reactions** are medical occurrences which are known to occur as a result of the intervention being tested.

7.2.1 Expected Adverse Events/Reactions

There are no anticipated adverse events in the population being studied.

7.2.2 Expected Serious Adverse Events

There are no anticipated SAEs in the population being studied.

7.3 Reporting procedures for All Adverse Events/Reactions

All non-serious Adverse Events/Adverse Reactions occurring from the time of start of study intervention until the end of the participants involvement in the study, observed by the investigator or reported by the participant, will be recorded.

The following information will be captured on the adverse event log;

- Description of the event
- Date of onset
- End date
- Severity*
- Assessment of relatedness to study (not related or related; possibly, probably unlikely)
- Action taken

Follow-up information will be provided as necessary.

The relationship of the event to the study will be assessed and signed off by a medically qualified individual listed on the Delegation of Authority and Signature Log.

Events will be followed-up until resolution or the event is considered stable.

It will be left to the investigator's clinical judgment whether or not an AE is of sufficient severity to require the participant's removal from the study (or the study intervention/procedures). A participant may also voluntarily withdraw from treatment/the study due to what he or she perceives as an intolerable AE. If either of these occurs, the participant must undergo an end of study assessment and be given appropriate care under medical supervision until symptoms cease or the condition becomes stable.

SPONSOR REFERENCE: 1097

OurPERSPECTIVE endometrial cancer survivorship Study

Protocol Version v1.0 14/10/2025

IRAS: 363748

*The severity of events will be assessed on the following scale: 1 = mild, 2 = moderate, 3 = severe.

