Study Participants	Women who have completed primary treatment for endometrial cancer within 36 months; no evidence of recurrence; able to provide consent; able to participate in English-language group sessions.	
Sample Size	Estimated 30 participants.	
Follow up duration	Follow up: 12 months	
Planned Study Period	February 2026 – January 2028	
	Objectives	End Points / Outcome Measures
Primary	
Is the OurPERSPECTIVE course acceptable and useful for women who have completed treatment for endometrial cancer?
	
The primary outcome is the acceptability and feasibility of the OurPERSPECTIVE survivorship course.
 
This will be assessed using:
 
 – Recruitment rates (proportion of eligible women approached who consent to take part). – Retention rates (proportion of participants completing the 8-week course). – Attendance and engagement (number of sessions attended). – Participant evaluation of the course (questionnaire ratings of usefulness and relevance, and qualitative feedback from focus groups). 
These measures will determine whether the intervention and study procedures are acceptable and feasible, and whether

SPONSOR REFERENCE: 1097

OurPERSPECTIVE endometrial cancer survivorship Study

Protocol Version v1.0 14/10/2025

IRAS: 363748

		progression to a full randomised controlled trial is justified.

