5.4 Study assessments

Demographic and Clinical Data

Demographic information (age, sex, ethnicity, postcode) and relevant clinical details (date of completion of primary treatment, cancer and stage, and current disease status) will be obtained from routine NHS clinical records at the University Hospitals of Leicester NHS Trust. Specifically, the following information will be sought:

Anthropometric Data: Height and weight will be measured and used to calculate Body Mass Index (BMI).

SPONSOR REFERENCE: 1097

OurPERSPECTIVE endometrial cancer survivorship Study

Protocol Version v1.0 14/10/2025

IRAS: 363748

Endometrial Cancer Data: Information will be collected on recurrence, definitive treatment undertaken, menopause status.

Medical History Data: Information on other medical conditions/medications will be collected, as well as smoking and alcohol intake questions.

Equity characteristics (modified PROGRESS-Plus): Information on equity characteristics and social circumstance will be collected, with the option of 'prefer not to say' provided for information deemed to be of a sensitive nature.

Baseline Questionnaires (Week 0)

At enrolment, participants will complete self-reported questionnaires delivered electronically or on paper (depending on participant preference). These will include:

- Quality of life: SF-36
- Psychological wellbeing: Hospital Anxiety and Depression Scale (HADS)
- Multi-dimensional health-related quality of life assessment: EQ-5D-5L
- Acceptability and usability questions tailored to the intervention

Midpoint Interview (Week 4)

At week 4, selected participants will be invited to take part in a short telephone interview to assess the feasibility and acceptability during the intervention. This will be with the research fellow. The interview will be recorded using Microsoft Teams.

Post-Intervention Questionnaires (3 months)

After completing the OurPERSPECTIVE course, participants will be asked to complete the same set of questionnaires as at baseline to assess feasibility of data collection and exploratory changes in quality of life, psychological wellbeing, and fear of recurrence. It is anticipated that this data collection will be approximately 3-months since recruitment. Additional acceptability and usability questions will capture participant feedback on the intervention as a whole. Further follow up questionnaires will be sent at the 6-month and 12-month point, respectively.

OurPERSPECTIVE Course Attendance

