Attendance at each of the 8 weekly online group sessions will be recorded in the case report form. Sessions will last approximately 60 minutes and will be facilitated by a gynaecology nurse specialist. Group rules will be set at the start, and each session will end with a short debrief, and mood self-rating in the accompanying guided workbook provided to patients. Participants will be given a workbook to support their attendance on the course and a separate reflective diary where they can document their thoughts, experiences and feedback of the different modules. The diary will be returned to the research team at the end of the course; however, the participants will be able to keep the course workbook.

SPONSOR REFERENCE: 1097

OurPERSPECTIVE endometrial cancer survivorship Study

Protocol Version v1.0 14/10/2025

IRAS: 363748

Focus Group

Within 4 weeks of course completion, participants will be invited to take part in a virtual focus group to provide qualitative feedback on their experience, the data collection from each participant will conclude at 3-months. Discussions will explore perceived benefits, challenges, and suggestions for improvement. Sessions will be audio recorded, transcribed, and anonymised for analysis. The number of participants in each focus group will be 4-6 in order give participants time and opportunity to share their experiences. For individuals who do not wish to discuss their experiences openly, the option of a one-one virtual or telephone interview with the research fellow will be offered.

Withdrawal or Early Exit

If a participant withdraws before completing the course, the reason (if provided) will be recorded. Participants will be asked if they are willing to complete an early-exit telephone interview in order to explore their reasons and what could be done to improve the course to reduce future withdrawals.

Mode of Delivery

All questionnaires will be completed remotely (online or postal). The OurPERSPECTIVE intervention and focus groups will be delivered virtually (videoconferencing platform). No face-to-face study visits are required.

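### After baseline no check of recurrence, admission or vital status is scheduled and section 7.4 holds no SAE procedure, so a death or serious illness can be counted as loss to follow-up

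*Protocol*

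**What the plan says.** **Recurrence and clinical data.** Section 5.4 states: "Information will be collected on recurrence, definitive treatment undertaken, menopause status". These items sit with the demographic and clinical data drawn from NHS records. The schedule in section 5.1 marks demographics and medical history at Baseline only. Section 4.1 admits only women without evidence of recurrence. Section 9.3 lists hospital records as a source for eligibility, diagnosis and treatment completion date, and names no follow-up use.

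**Later recurrence.** Section 5.7 lets the Principal Investigator withdraw a participant on grounds such as "e.g. recurrence of cancer, significant health deterioration, or safeguarding concerns". The type of withdrawal and its reason go in the CRF and the enrolment log.

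**Adverse events.** Section 7.3 covers non-serious events from the start of the intervention to the end of the participant's involvement, and those "observed by the investigator or reported by the participant, will be recorded". Section 7.1 makes death and inpatient admission serious. Section 7.4, headed as the reporting procedure for serious events, contains urgent-safety-measures text that section 7.5 nearly repeats.

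**Loss to follow-up.** Section 5.4.1 states: "Participants will be considered lost to follow-up if they do not return post-intervention questionnaires and cannot be contacted after three attempts".

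**End of data collection.** The focus group paragraph of section 5.4 says "the data collection from each participant will conclude at 3-months". Section 5.8 ends the study, in practical terms, with "the return of the post-intervention questionnaires at the 12-month mark".

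**The concern.** The events that matter most for safety, and for interpreting dropout, are those a woman is least able to report herself. Follow-up is remote. The forms described are SF-36, HADS, EQ-5D-5L and acceptability questions, and none is described as asking about new illness or admission. The plan schedules no other look at what has happened to her.

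Two things are at stake. First, the follow-up and questionnaire-completion figures are secondary outcomes meant to inform a later randomised trial. If death or serious illness is pooled with disengagement, that trial inherits the wrong reasons for attrition. Second, reminders by email, telephone or post may go to a bereaved household or to a woman who is seriously ill, although the treating hospital may already hold the information.

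**Working it through.** **1. The plan's own figure.** The study summary gives "Estimated 30 participants". Section 5.5.1 says "The courses will aim to have 10 women per cohort, with 3 cohorts planned for the feasibility study". 3 × 10 = 30, so the size is reproduced. It is described as pragmatic, so there is no power calculation to check.

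**2. What each route captures, with the passages side by side.**

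| Event after baseline | Route described | Gap |
|---|---|---|
| Recurrence | Withdrawal reason (5.7) | Needs someone to notice it and withdrawal to follow; no scheduled check |
| Non-serious event | Observed or reported (7.3) | Passive |
| Admission | SAE by definition (7.1) | No SAE procedure in 7.4 |
| Death | SAE by definition (7.1) | No SAE procedure in 7.4; no vital-status check in 5.4.1 |

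**3. The lost-to-follow-up rule applied literally.** It has two conditions: no returned form, and no contact after three attempts. A woman who has died, or is too ill to respond, can meet both. A woman who has relapsed or been admitted but answers the telephone does not meet the second and is not lost.

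**4. Length of the window without planned live contact.** This depends on which end date applies.
- Twelve months counted from course end: 8 + 52 = 60 weeks. The course (8 weeks) plus the focus group (within 4 weeks) gives 12 weeks. (60 − 12)/60 = 48/60 = 80%.
- Twelve months counted from recruitment: (52 − 12)/52 = 40/52 = 77%.
- Data collection ending at about 3 months from recruitment: the gap largely disappears.

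Because the protocol gives both ends, none of these can be taken as the figure. Reminder calls also provide some contact within the gap.

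**5. Chance that at least one event occurs.** The protocol gives no 12-month risk of death, recurrence or admission, so the risk p is an assumption, shown over a range. Formula: 1 − (1 − p)^30; expected number: 30p.

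| Assumed p | Expected events | P(at least one) |
|---|---|---|
| 1% | 0.3 | 26% |
| 2% | 0.6 | 45% |
| 5% | 1.5 | 79% |
| 10% | 3.0 | 96% |
| 15% | 4.5 | 99% |

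These are chances that an event happens, not that it is missed or misfiled. The documents give nothing from which the latter could be computed.

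**6. Effect of misfiling.** With a denominator of 30: 1/30 = 3.3 percentage points, 2/30 = 6.7, 3/30 = 10.0.

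**7. Which outcome moves.** Sections 2 and 8.3.2 define primary retention as completion of the 8-week course, a period of weekly nurse-led sessions. Misfiling at the 3-, 6- or 12-month mailings therefore falls on follow-up and questionnaire completion.

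**The case against.** The best defence is that this is a low-risk educational course run through the treating hospital. The facilitating nurse belongs to the direct care team and is known to the women (section 5.5.1), a study team member in direct care has record access (section 5.2.1), and standard follow-up already looks for recurrence (section 5.4.1). Section 7.3 also includes events that the investigator observes. News of a recurrence may well reach the study.

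Much of this stands, and it rules out several stronger readings. A reader might infer that recurrence can be recorded only at baseline; section 5.7 contradicts that, because it is recorded later if it leads to withdrawal. A reader might take the section 7.3 sentence as the reason deaths and admissions are missed; it covers non-serious events only, and the defect for serious events lies in section 7.4. A reader might infer that every relapsed or admitted woman becomes lost to follow-up; one who is reached by telephone does not. The absence of an adverse event row in the schedule is also weak evidence, since that table has no rows for course sessions and no 12-month column.

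What the defence does not supply is a stated link. Section 5.7 says what may follow once recurrence is known, not how the study learns of it. The information flow it describes runs from study to clinic: the specialist nurses will know of a withdrawal. No passage sends a death, recurrence or admission from the clinical record to the study, and nothing elsewhere fills the gap in section 7.4.

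**Conclusion.** The concern holds in limited form. After baseline the protocol describes no scheduled check of recurrence, admission or vital status. Serious events have no recording procedure, because section 7.4 holds other text. The lost-to-follow-up rule, followed as written, can count a woman who has died or is too ill to reply as lost. The adverse event window has no single end.

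The size is 3.3 percentage points per misfiled woman, assuming a denominator of 30. It applies to the 3-, 6- and 12-month follow-up and completion figures and to the reasons given for attrition. It would be tempting to conclude that the primary retention result is biased, or that the 26% to 99% range is the chance of a missed event. The documents support neither: primary retention is 8-week completion, and the range is the chance of an event occurring under assumed risks of 1% to 15%. Nor is an event rate among the stated outcomes. This is a worthwhile and cheap correction, not a threat to the study's main conclusion.

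**What to change.** 1. Have the direct care team check the hospital record for vital status, recurrence and admission before each 3-, 6- and 12-month mailing or reminder and at study end, and enter the result in the CRF. Add this use of hospital records to section 9.3.
2. Amend the lost-to-follow-up rule in section 5.4.1 so that death and recurrence are reported as categories separate from loss.
3. Replace the misplaced text in section 7.4 with the procedure for recording and reporting serious events.
4. Reconcile the 3-month end in section 5.4 with the 12-month end in section 5.8, so that the adverse event window in section 7.3 has one end.

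**Cost.** At one check per woman per round, 30 × 3 = 90 checks for the three mailings, or 30 × 4 = 120 with a separate check at study end. Repeat checks before reminders to non-responders would add to this. All are short and done by staff who already have access. The change also needs protocol wording, one CRF page, and confirmation that consent covers record access during follow-up.
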